## **5.2 Justification for Design (Population, Dose, etc.)**

### **5.2.1 Justification for Overall Study Design**

This is a randomized, double-blind, placebo parallel-controlled phase II clinical trial, which is planned to enroll 150 PD subjects. Subjects who are successfully screened will be randomized, and the efficacy will be evaluated after oral administration for 12 consecutive weeks and subjects will continue to be followed up for 1 week after the end of treatment. Male or female subjects aged between 30 and 80 years (both inclusive) will be included in this study, including elderly subjects. Based on the PK model, the PK profile of TJ0113 following the oral administration at doses of 80 mg, 160 mg, and 400 mg in the elderly population (65, 70, and 80 years) is speculated to be similar to that of adult subjects.

### **5.2.2 Justification for Dose**

The proposed doses of TJ0113 capsules for this study are 200 mg QD and 400 mg QD. The dose design is primarily based on the results of non-clinical pharmacology studies of TJ0113 and the currently completed phase I study.

The PD studies of compound TJ0113 in the MPTP-induced mouse PD model and the study of the mitochondrial repair effect of compound TJ0113 in the MPTP-induced mouse PD model indicated that TJ0113 has different degrees of therapeutic effect on PD model within the dose range of 10, 30, and 60 mg/kg once daily. Based on this data, the human equivalent dose (HED) calculated by the body surface area normalization method was 0.9, 2.7, and 5.4 mg/kg, respectively and 54, 162, and 324 mg based on an adult body weight of 60 kg.

The PD study of TJ0113 in the 6-OHDA-induced rat PD model suggested that TJ0113 had different degrees of therapeutic effect on the PD model at doses of 5, 15, and 30 mg/kg once daily. Based on this data, the HED calculated by the body surface area normalization method was 0.8, 2.5, and 4.9 mg/kg, respectively, and 48, 150, and 294 mg based on an adult weight of 60 kg.

In the kinetics study in the plasma of rats (TJ22039PKAB18), the results of the mean plasma PK parameters of the unchanged drug after single oral gavage administration to SD rats

showed that the  $AUC_{0-24h}$  was  $10.7 \pm 4.44 \text{ h}\cdot\mu\text{g/mL}$  in the 10 mg/kg dose group and  $22.1 \pm 6.66 \text{ h}\cdot\mu\text{g/mL}$  in the 30 mg/kg dose group. The results of phase I clinical trial of TJ0113 were as follows: the  $AUC_{0-\text{last}}$  of the SAD study was  $8,570.86 \pm 2,413.178 \text{ h}\cdot\text{ng/mL}$  in the 260 mg dose group and  $12,785.99 \pm 4,491.670 \text{ h}\cdot\text{ng/mL}$  in the 400 mg dose group. Combined with the PD study of the 6-OHDA-induced rat PD model, both the 200 mg and 400 mg dose levels are expected to be within the clinically effective dose range.

In addition, data from the phase I study of TJ0113 showed that following the single dose administration within the dose range of 80-720 mg, and the multiple dose administration at 200 mg QD, 400 mg QD, and 300 mg BID, the safety profiles of TJ0113 capsules were favorable and the incidence of AEs were similar between the treatment group and the placebo group. Within the dose range of 80-400 mg, the exposures ( $AUC_{0-\text{last}}$  and  $AUC_{0-\text{inf}}$ ) increased in a linear fashion. After 200 mg QD administration, TJ0113 basically did not accumulate in vivo; after 400 mg QD administration, there was a slight accumulation of TJ0113 in vivo.

In summary, combined with the current strength (100 mg) and clinical compliance of TJ0113 capsules, the proposed doses for this study are 200 mg QD and 400 mg QD.

### **5.3 Randomization and Blinding**

#### **5.3.1 Randomization**

After subjects enter the screening period, the screening numbers will be assigned strictly according to the sequence of study entry. The screening numbers will be expressed by five Arabic numerals, the first two digits are the site number, and the last three digits are the screening sequence number. For example, the screening number for the first subject in Site 01 is 01001. Once the subject is assigned with a number, the number cannot be reused.

Subject randomization numbers and drug randomization numbers are compiled by project-independent randomization statisticians from the Statistics Department. The randomization statistician generates a subject randomization list and a drug randomization list using the SAS 9.4 or later PLAN process. It is planned to include approximately 150 subjects who will be randomized in a 1:1 ratio into two cohorts (Cohort 1: 200 mg dose group; Cohort 2: 400 mg dose group). Within each cohort, subjects who have been successfully screened will be randomly assigned to TJ0113 capsules group and the placebo group in a ratio of 2:1 within each stratum based on a stratification factor whether they have been receiving levodopa, the background medication for PD (yes vs. no) at a stable dose. Among them, approximately 50 subjects will receive TJ0113 capsules and approximately 25 subjects will receive the placebo. The subject randomization list and drug randomization list will be imported into the

Interactive Web Response System (IWRS) by the system director. For subjects who have been successfully screened, the randomization number of the subjects will be obtained by the investigator through the IWRS, and the subjects will enter the corresponding group according to the randomization number. Subjects who withdraw from the study midway will not be allowed to re-enter the study. The specific randomization procedure will be described in the randomization protocol.

### **5.3.2 Blinding**

The blinding of this study is completed under the guidance of a randomized statistician independent of the statistical analysis of this project, and the electronic blind code will be kept by the randomized statistician in a folder with permission control.

During the treatment period, in order to maintain the double-blind status of the study, the packages for investigational drug and placebo will be identical in physical appearance. The sponsor, investigators and other personnel involved in the assessment of subjects and implementation of the trial will not be aware of the distribution of therapeutic drugs.

Throughout the study, all personnel involved in blinding should remain blinded until the database is locked.

#### **5.3.2.1 Blinding Implementation**

The placebo has the same dosage form, appearance, strength, color, weight, smell and taste as the investigational drug, and does not contain any active ingredients. The packages for investigational drug and placebo will be identical in physical appearance to ensure the implementation of the blinding method. The sponsor or its designee will assign a blind code to the investigational drug and placebo.

Subjects who meet all inclusion criteria and none of the exclusion criteria will be randomized. For subjects who require to be randomized and dispensed with drug, the information of randomization number, randomization time, drug number and drug dispensing time are all provided by the Clinflash drug dispensing system. The investigator or his/her designee will log in to the Clinflash IRT system, obtain the information of the randomization number and the corresponding drug number, and distribute the corresponding investigational product according to the drug number.

#### **5.3.2.2 Unblinding Provisions**

The database will be locked when all eCRF data are entered and signed as well as reviewed in a blinded manner, the analysis population is determined, and the statistical analysis plan (SAP)

is signed. After the database is locked, unblinding is carried out to determine the subject group, and the unblinding record is kept. The unblinding must be signed and confirmed by the sponsor and the statistician.

### **5.3.2.3 Emergency Unblinding**

Emergency unblinding refers to obtaining the treatment grouping information of individual or some subjects in emergency through pre-established standard operating procedures based on the safety considerations of subjects and other special reasons in accordance with the clinical trial protocol. It should only be performed if the investigator must know the treatment grouping information of the subject who experiences an emergency (e.g., when the subject experiences an SAE or is in urgent need of rescue treatment). There is no need for emergency unblinding, if it is known that the treatment grouping information is not necessary for management of the emergency.

In the event of emergency unblinding, it is necessary to timely record the time, reason and operator of emergency unblinding, notify the CRA as soon as possible, and submit the safety event report to the Ethics Committee. Upon emergency unblinding, the subject must terminate the treatment. The investigator should record the reason for termination of treatment in the case report form.

In addition, if an unexpected serious adverse event occurs, the Pharmacovigilance Department should also unblind the individual subjects according to the corresponding procedures.

## **5.4 Definition of End-of-Study (EOS)**

The end of the study (EOS) is when the last subject has his/her last study visit, unless the EOS is caused by a condition described in [Section 4.5](#) (Criteria for Study Termination/Site Closure).

The EOS for an individual subject is defined as when the subject completes V7 or is early withdrawn from the study (see [Section 4.4](#) for criteria for early withdrawal). For subjects who early withdraw from the study, the date on which the last visit is completed or the last contact is made is the date of EOS (whichever occurs later).

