Collection of blood samples for exploratory analysis (genomic resequencing)		X b				X		X
Exploratory skeletal muscle mass and function assessment (ASMI, grip strength and 6-meter walking speed test) 		X				X		X
Assessment using modified Hoehn and Yahr Scale	X							
MDS-UPDRS score 	X	X	X	X	X	X		X
Dispensing of investigational product		X	X	X	X			
Return of investigational product				X	X	X		X
Administration of investigational product			The first dose will be administered on D1 and the last dose on D84. Take orally on an empty stomach in the morning, once daily. Fast for half an hour after oral administration. At site visits, it should be administered together with the background medication for PD. It is recommended that subjects should take the drug at the same time ± 1 h each day as much as possible.					

Study Process	Screening period		Treatment period				Follow-up Period (Telephone)	Early Withdrawal Visit 
Visit No.	V1	V2	V3	V4	V5	V6	V7	-
Visit duration (W)	W-4~1	W-1	W1	W4	W8	W12	W13	-
Visit duration (D)	D-28~2	D-1	D7	D28	D56	D84	D91	-
Window period (days)	-	-	±1	±2	±2	±2	±3	-
Dispensing of diary cards/instructions for completion		X	X	X	X			
Return of diary cards			X	X	X	X		X
Concomitant Medication	X	X	X	X	X	X	X	X
AEs	X	X	X	X	X	X	X	X

Note:

- a. If hematology, blood chemistry, coagulation function test, urinalysis, 12-lead ECG examinations, weight measurement and calculations of creatinine clearance (Ccr) have been performed within 7 days (exclusive) before D-1, these tests are not required to be repeated on D-1; otherwise, they are required to be re-tested on D-1 and the eligibility for the study entry should be confirmed according to the test results.
- b. Collection of blood samples for exploratory analysis of genomic resequencing: each subject will be collected once at V2 (if not collected at V2, it is allowed to be supplemented at V6 or early withdrawal visit).

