##### Follow-up period (1 week, telephone follow-up)

Follow-up will be continued for 1 week after the end of the treatment period, and AE and concomitant medication information will be collected via telephone follow-up. If an AE/SAE occurs during the study, it will be followed up by the investigator until it has been clinically recovered, stabilized, returns to the screening or baseline level (if baseline level is known), the subject is lost to follow-up (e.g., no more information is available or the subject/caregiver refuses to provide any information), or dead.

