#### **8.7.2.3 V6 (D84, W12)**

At V6, the following procedures will be performed:

- Subjects must be fasted before each visit (fast for at least 10 hours overnight without depriving of water);
- Vital signs;
- Physical examination;
- 12-lead ECG;
- Laboratory tests: including hematology, blood chemistry, urinalysis, coagulation function test, and urine pregnancy test (only for women of childbearing potential);
- Weight measurement and Ccr calculation;

- Collect blood samples for exploratory analysis (one blood sample each for inflammatory indicators and PD biomarkers; among these, 5 mL of blood is collected for PD biomarker testing and sent to the central laboratory for testing);
- Exploratory skeletal muscle mass and function assessment: including ASMI, muscle strength (grip strength) and 6-meter walking speed test (specific test indicators are subject to the actual operation of each center). Among them, ASMI is detected and calculated by DXA, and the calculation formula is ASMI = appendicular muscle mass (kg) / height (m^2);
  - Return investigational product;
- Return diary card;
- MDS-UPDRS Part III score before administration of the investigational product and the background medication for PD (if applicable) ( $\geq$  12 hours from the most recent administration of background medication for PD (if applicable) and the investigational product);
- Take investigational product and background medication for PD (if applicable) concomitantly;
- MDS-UPDRS Part III score after administration of the investigational product and the background medication for PD (if applicable) (to be performed at  $2 \pm 1$  hours after the administration);
  - MDS-UPDRS Parts I, II, and IV scores;
  - Record concomitant medications/therapies;
  - Record AEs;

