## **9.4 Collection, Recording and Reporting of AEs**

### **9.4.1 Collection and Recording of AEs and SAEs**

#### **9.4.1.1 Collection Time of AEs**

AEs are collected in this trial from the time the subject receives the investigational product (i.e., TJ0113 capsules or placebo) until the end of the follow-up period. Supplementary description is as follows:

- Untoward medical occurrences (including abnormalities at baseline) that newly occur or worsen relative to pre-signing state from subject's signing ICF to the first dose of the investigational product, if assessed by the investigator as related to the subject's participation in this trial (such as a protocol-specified procedure or invasive test), should be recorded and reported as AEs, otherwise should be recorded as medical history;
- The investigator needs to collect all AEs (regardless of whether it is causally related to the investigational product or related to clinical procedure) from the first dose of the investigational product to the end of the follow-up period;
- AEs that occur after the follow-up period must also be collected and recorded if the investigator considers that it is related to the investigational product (including SAEs) after awareness.

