## **12.7 Protocol Deviations**

The investigator has to conduct this clinical trial according to the clinical study protocol approved by the EC and GCP regulations. The protocol is established to make the investigator follow regulations in ICH E6 Section 4. During the trial, the investigator should avoid protocol deviations, except emergency actions taken to avoid direct harm to subjects. In case

of other unexpected situation requiring deviation from protocol-specified procedures, the investigator should discuss with the medical personnel (and the Ethics Committee when necessary) to determine appropriate measures.

All protocol deviations should be recorded by the study site, including but not limited to time of protocol deviation, time of awareness, description of event and action taken. In case of a significant protocol deviation, the medical personnel, CRA, and EC should be notified in a timely manner.

If a subject withdraws from the trial early due to withdrawal of consent or loss to follow-up, and fails to complete the early withdrawal visit and post-treatment follow-up as specified in the protocol, it will not be recorded as a protocol deviation, but the investigator must make corresponding records in the medical records.

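### Post-treatment AE follow-up is stated as 1 week, but V7 is timed from Day 1, and early withdrawals have no contact scheduled at a defined interval after the last dose

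*Protocol*

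**What the plan says.** **Completers.** Protocol 5.1.2 states: "Follow-up will be continued for 1 week after the end of the treatment period". The follow-up is the V7 telephone call, which collects AEs and concomitant medication (8.7.3). The Schedule of Activities (1.2) sets the visit days as "Visit duration (D) D-28~2 D-1 D7 D28 D56 D84 D91" and the windows as "Window period (days) - - ±1 ±2 ±2 ±2 ±3", so V6 is D84 ± 2 and V7 is D91 ± 3. The schedule also says "The first dose will be administered on D1 and the last dose on D84". The V6 procedures in 8.7.2.3, however, include "Take investigational product and background medication for PD (if applicable) concomitantly", which ties a dose to the actual day of V6.

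**Early withdrawals.** Section 5.4 says: "The EOS for an individual subject is defined as when the subject completes V7 or is early withdrawn from the study". It dates that end by the last visit or last contact, whichever is later. Sections 4.4 and 8.7.4 ask for an early withdrawal visit within 7 days of the investigator's awareness, and 8.7.4 has AEs recorded there. Section 8.7.4 does not require the visit after consent withdrawal or loss to follow-up. Section 12.7 speaks of an early withdrawal who "fails to complete the early withdrawal visit and post-treatment follow-up as specified in the protocol".

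**Collection rules.** Sections 9.4.1.1 and 9.4.2 collect all AEs and SAEs, whatever the cause, from first dose to the end of the follow-up period. After that, 9.4.1.1 says: "AEs that occur after the follow-up period must also be collected and recorded if the investigator considers that it is related". For SAEs after follow-up, 9.4.2 asks for a report if a relation to the product cannot be ruled out.

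**The concern.** Safety is a secondary objective, and the SAP (6.12.2) compares the arms through counts and percentages of subjects with TEAEs and SAEs. The SAP's TEAE definition (3.3.1) has a start, the first dose, but no end. The protocol's collection rules therefore decide how long each subject is observed for events of any cause.

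Two things make that period uneven. For completers it depends on where two visit windows fall. For early withdrawals its end is either the withdrawal itself or a follow-up that one section mentions and no section schedules.

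The second matters more. Section 4.4 lists QTcF, hepatic and intolerable events as grounds for withdrawal from the study, not only from treatment, and 2.5.1 names QT, liver and kidney among the risks. A subject who leaves on such grounds does not proceed to V7. If more subjects stop early in one arm than in another, the arms would differ in how long all-cause events are sought after the last dose.

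**Working it through.** **1. The plan's own figure.** V7 day minus V6 day = 91 − 84 = 7 days. This reproduces the stated 1 week.

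**2. Range for completers, last dose taken at V6.** V6 window: 84 ± 2 = D82 to D86. V7 window: 91 ± 3 = D88 to D94.
- Shortest gap: 88 − 86 = 2 days.
- Longest gap: 94 − 82 = 12 days.

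**3. Range for completers, last dose fixed at D84 as the schedule states.**
- Shortest gap: 88 − 84 = 4 days.
- Longest gap: 94 − 84 = 10 days.

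**4. How often the windows fall short of a week.** There are 5 × 7 = 35 permitted pairs of V6 and V7 days. Of these, 15 give less than 7 days, 5 give exactly 7 and 15 give more, with an unweighted mean of 7.0 days. This counts permitted combinations and does not forecast attendance.

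**5. The two dosing statements.** A last dose on D84 and a dose on site at V6 agree only when V6 is held on D84. If V6 is on D82 or D83, a last dose on D84 comes after V6. If V6 is on D85 or D86, the on-site dose comes after D84. The two passages have to be reconciled.

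**6. Early withdrawals, section by section.**
- 4.4 and 8.7.4: one visit, 0 to 7 days after awareness. Its distance from the last dose is not set. It is 0 days if the last dose, awareness and visit fall on the same day, and it can exceed 7 days if awareness comes late.
- 8.7.3: V7 is given only as D91, W13, with no version for a subject who stopped earlier.
- 5.4: the subject's study ends at V7 or at early withdrawal.
- 12.7: presupposes both an early withdrawal visit and a post-treatment follow-up for these subjects.

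The first three sections schedule no follow-up after the withdrawal visit, while the fourth treats one as specified. They do not agree.

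**7. The protocol already uses the last dose as an anchor.** Sections 7.2.1 and 7.2.2 run the concomitant-medication rules to 1 week after the last dose. No scheduled contact covers that week for early withdrawals, and for completers V7 can come before it ends (steps 2 and 3).

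**8. What follows for AE collection.** Up to the end of follow-up every AE counts. Beyond it, an AE is recorded only if judged related, and an SAE is reported only if relatedness cannot be ruled out. Where that switch falls for an early withdrawal is not defined.

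**The case against.** The strongest reply is that early withdrawals are not neglected, and much of it stands.

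- A reader might infer that those who stop early get no contact after the last dose. The documents do not support this. The early withdrawal visit records AEs and includes examination, ECG and laboratory tests, which V7 does not. The waiver for a visit less than 7 days earlier covers repeated tests, not AE recording. Section 5.4 foresees a later contact when it dates the end of study.
- Subjects withdrawn for an AE or SAE are followed until recovery, stabilisation, return to baseline, loss to follow-up or death (4.4). Strictly this covers the known event, but it keeps a line open through which new events may be heard of. Related events recorded later still count as TEAEs, since the SAP definition has no upper limit.
- Section 5.1.2 does not restrict the follow-up week to completers. One fair reading is that it applies to everyone and has simply not been put into the schedule.
- The 2-day and 12-day gaps are the extreme corners of two ordinary windows. In a double-blind trial there is no evident reason for that variation to differ by arm.
- With a phase I half-life of about 2.24 to 3.20 h, 2 days (48 h) is 48/3.20 = 15.0 to 48/2.24 = 21.4 half-lives of parent drug. This does not exclude delayed organ effects, but a telephone call would not itself detect a silent liver or QTc change.

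What the reply does not meet is the absence of any contact timed from the last dose for early withdrawals, the disagreement between 5.4, 8.7.4 and 12.7, and the causality filter that begins at an undefined point.

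**Conclusion.** The point holds as an inconsistency with a practical consequence. For completers the stated week is met nominally (7 days), but a compliant V7 can come 2 to 12 days after the last dose, or 4 to 10 days if the last dose is fixed at D84. For early withdrawals no contact is scheduled at a defined interval after the last dose, and the sections disagree on whether post-treatment follow-up exists. A site following the plan as written can therefore give early stoppers a shorter all-cause window, followed by one limited by relatedness.

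A reader might go further and infer that delayed harms are under-counted, or that an active arm's TEAE and SAE rates are biased downward. The documents do not support that. They give no early-stopping rate by arm and no signal of delayed harm, so neither size nor direction can be computed. For scale only, with about 50 subjects per arm, one subject whose only event is missed changes that arm's incidence by 1/50 = 2 percentage points. That is not an estimate of how many would be missed.

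The range of 2 to 12 days assumes that the V6 dose is the last dose and that V7 is counted from Day 1. The concern about unequal ascertainment matters only if early stopping differs between arms. The change is worth making because it is specific and cheap.

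**What to change.** 1. In 1.2 and 8.7.3, time the V7 call from the actual last dose, using the protocol's own 1 week, so that the call does not fall before that week ends.
2. In 1.2 and 8.7.4, make the same call to every dosed subject who withdraws early and has not refused contact. The early withdrawal visit stays as it is.
3. In 9.4.1.1 and 9.4.2, end all-cause AE and SAE collection at that contact for completers and early withdrawals alike, keeping the existing rules for later events.
4. Align the end-of-study definition in 5.4 and the wording of 12.7 with this.
5. Reconcile the schedule's statement of the last dose on D84 with dosing at V6 in 8.7.2.3. Which statement should stand is for the sponsor to decide.
6. As a consequential edit, have SAP 3.3.1 state the end of the TEAE window, measured from the last dose and the same for both groups.

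The cost is protocol and SAP wording, about one telephone call per early withdrawal, and a shift of a few days in V7 for some completers. No site visit or test is added.
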